5.3 Unscheduled Visits

Unscheduled visits will be handled on a case by case basis dependent upon the reasoning for the patients' visit. If subjects are displaying signs of immediate danger or instability, they will be referred to emergency department or directly admitted. However, unscheduled visits are rare for this type of procedure.

5.4 Subject Withdrawal

Subjects may withdraw from the study at any time without impact to their care. They may also be discontinued from the study at the discretion of the Investigator. Subjects may also be withdrawn following an adverse event that does not allow them to continue with the study. It will be documented whether or not each subject completes the study. Subjects who withdraw early will have one final communication to collect final evaluations and assess for adverse events.

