3.4 Study Endpoints

3.4.1 Primary Study Endpoint

The primary endpoint is volume changes of the infraorbital area over time after injection of filler quantified using 3D facial imaging measurements.

CONFIDENTIAL

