4.1 Duration of Study Participation

The duration of study participation is 90 days. Subjects will receive injections on day 1, and follow up imaging will occur on day 14, 30, and 90 post intervention. Each individual subject's participation time in the study will consist of the duration of the initial imaging session (approximately 20 minutes), procedure (15 minutes), follow up imaging (20 min).

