5.4.1 Data Collection and Follow-up for Withdrawn Subjects

Patients must document in a letter asking not to use the data collected and formalize the withdrawal. Otherwise, data up until withdrawal will be available for analysis.

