6.1 Sample Size and Power Determination

The sample size of this case series will be 10 female patients between the ages 22 and 65.

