7.2 Recording of Adverse Events

At each contact with the subject, the investigator will seek information on adverse events by specific questioning and, as appropriate, by examination. Information on all adverse events will be recorded immediately in the source document, and also in the appropriate adverse event module of the case report form (CRF). All clearly related signs, symptoms, and abnormal diagnostic procedures results should be recorded in the source document, though should be grouped under one diagnosis.

All adverse events occurring during the study period will be recorded. The clinical course of each event will be followed until resolution, stabilization, or until it has been determined that the study intervention or participation is not the cause. Serious adverse events that are still ongoing at the end of the study period will be followed up to determine the final outcome. Any serious adverse event that occurs after the study period and is considered to be possibly related to the study intervention or study participation will be recorded and reported immediately.

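### After a one-time Day 1 injection, discontinuing a subject under 5.4 can only end data collection: later 3D volumes are lost and new adverse events are no longer actively sought

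*Combined protocol and SAP*

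**What the plan says.** Section 4.1 sets out the whole course: "Subjects will receive injections on day 1, and follow up imaging will occur on day 14, 30, and 90 post intervention". Section 5.2 and the schedule of procedures add no further injection. Visits 2 to 4 consist of VECTRA imaging, FACE-Q and adverse-event assessment.

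Section 3.4.1 defines the outcome: "The primary endpoint is volume changes of the infraorbital area over time after injection of filler quantified using 3D facial imaging measurements".

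Section 5.4 gives three routes out of the study: the subject's own choice, the investigator's discretion (no criteria given), and an adverse event: "Subjects may also be withdrawn following an adverse event that does not allow them to continue with the study". After any of them: "Subjects who withdraw early will have one final communication to collect final evaluations and assess for adverse events". Section 5.4.1 deals with data already collected. Unless the subject objects by letter, "Otherwise, data up until withdrawal will be available for analysis". Section 5.5, although titled for early termination visits, schedules no visit.

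Section 7.2 requires all events in the study period to be recorded and adds: "The clinical course of each event will be followed until resolution, stabilization, or until it has been determined" that the study was not the cause. Section 7.4.1 requires every serious event to be followed until it is resolved or stable. Neither section exempts withdrawn subjects, and neither is mentioned in 5.4. Section 6 contains no missing-data rule.

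**The concern.** Where treatment is repeated, withdrawing a subject can serve to stop exposure. Here there is no later dose to stop, so for an injected subject the only effect is that imaging, questionnaires and adverse-event questions end. Volume by 3D imaging cannot be obtained from a communication, so the primary endpoint is missing at every visit after the withdrawal date.

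The missing values may not be a random subset. Section 9.1 lists swelling, firmness and lumps among the known effects, and these could plausibly alter a surface-volume measurement. The study is single-arm, so the investigator knows the treatment and can see the result when using discretion. If such subjects leave, the later part of the volume curve describes those who stayed. With a purely descriptive analysis and no missing-data rule, that completer mean is what would be reported.

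On safety, once the closing contact has been made, nothing in 5.4 to 5.5 plans for anyone to ask a withdrawn subject about new events up to Day 90. Staff reading 5.4 alone might also take the closing contact as the end of follow-up for an open event, which 7.2 does not allow.

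**Working it through.** There is no derived figure in the plan to reproduce. Section 6.1 states only "The sample size of this case series will be 10 female patients between the ages 22 and 65", with no SD, effect size or dropout rate. The check therefore has two parts.

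**1. What a discontinuation after injection removes**

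| Item | Status after discontinuation | Source |
|---|---|---|
| Study treatment | Already complete; nothing to stop | 4.1, 5.2 |
| Images and FACE-Q before withdrawal | Kept unless the subject objects in writing | 5.4.1 |
| 3D images after withdrawal | None provided for | 5.4, 5.5 |
| FACE-Q | Could be part of the closing evaluations, since follow-up FACE-Q is electronic | 5.4, 7.7 |
| Event that led to withdrawal | Recorded and followed | 7.2; 7.4.1 if serious |
| New events after the closing contact | Not actively sought | 5.4 names one contact only |

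**2. Size**

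Inputs from the plan: n = 10 (6.1) and 3 post-injection visits (4.1), so 10 x 3 = 30 planned follow-up imaging visits.

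Share lost: one withdrawal is 1/10 = 10% of the cohort at each later visit. The images lost are 3 of 30 if she leaves before Visit 2, 2 of 30 if between Visits 2 and 3, and 1 of 30 if between Visits 3 and 4.

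Shift in the mean: let k be the number withdrawn and d the difference between the mean volume change of those who stay and that of those withdrawn, in SD units.

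- Full-cohort mean = [(n - k) x completer mean + k x withdrawn mean] / n
- Completer mean minus full-cohort mean = (k/n) x d

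The documents give no value for d, so a range is assumed:

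| Assumed d | k = 1 | k = 2 |
|---|---|---|
| 0.5 SD | 0.1 x 0.5 = 0.05 SD | 0.2 x 0.5 = 0.10 SD |
| 1 SD | 0.1 x 1 = 0.10 SD | 0.2 x 1 = 0.20 SD |
| 2 SD | 0.1 x 2 = 0.20 SD | 0.2 x 2 = 0.40 SD |

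Chance that it happens at all: with an assumed per-subject risk p of such a withdrawal, the chance of at least one among 10 is 1 - (1 - p)^10. That gives 9.6% for p = 1%, 18.3% for 2%, 40.1% for 5%, 65.1% for 10% and 89.3% for 20%. The documents give no value for p either.

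**The case against.** The strongest reply is that the safety data are already protected. The event behind a withdrawal is recorded under 7.2 and followed to an endpoint; a serious event is covered again by 7.4.1; earlier data are kept; and the closing contact itself assesses adverse events. This stands. A reader might infer that the worst outcomes drop out of the safety data, but the documents do not support that. The safety gap is limited to new events after the closing contact.

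A reader might also infer that 5.4 contradicts 7.2. It does not: 5.4 never says that follow-up of an open event stops, and one closing study contact is compatible with continued follow-up of that event. The fault is a missing cross-reference, which leaves room for misreading.

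Third, the adverse-event clause is permissive and limited to events that prevent continuing. Lumps or swelling do not obviously prevent a 20-minute imaging session, and an event that truly prevents attendance causes a loss that no wording recovers. This stands as a limit on how often the problem will arise. It does not touch the discretion clause, which has no criteria, and 5.4 does not say what counts as unable to continue when continuing means imaging and a questionnaire.

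Fourth, that withdrawn subjects have different volumes is plausible but not documented, and the study disclaims statistical significance in 6.2. Both are true. No test is biased; what is at risk is the description itself.

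Finally, discretion has legitimate uses. Section 4.4 excludes other filler or neurotoxin injections during the study, and later images of such a subject would not show this product alone. That is a good reason not to remove discretion outright.

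**Conclusion.** The point holds as a low-cost improvement. It is certain from the text that discontinuation after Day 1 stops no study treatment and that 5.4 provides no imaging afterwards. Only visits after the withdrawal date are affected, so it would be wrong to say that the whole Day 14 to Day 90 record is lost.

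Each withdrawal costs 10% of the cohort at later visits. The resulting shift in the reported mean is 0.05 to 0.20 SD for one withdrawal and 0.10 to 0.40 SD for two. These shifts rest on an assumed difference of 0.5 to 2 SD between withdrawn and remaining subjects, and on the loss being related to outcome. The documents establish neither, and they give no expected withdrawal rate. Confidence is high on the lost images and moderate on how staff would read 5.4 beside 7.2.

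**What to change.** In 5.4:

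- Separate the subject's withdrawal of consent from discontinuation started by the investigator or by an adverse event.
- State that an injected subject who still consents and is able to attend continues the scheduled imaging, FACE-Q and adverse-event assessments at Visits 2 to 4.
- Offer 3D imaging at any final contact.
- Cross-refer to 7.2 and 7.4.1, and reconcile the three sections so that it is clear what the closing contact does and does not end.
- Keep investigator discretion.

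In Section 6, report the number imaged and the reasons for missing images at each visit. Flag images taken after an event was treated or after another filler or neurotoxin injection.

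The cost is protocol wording. Visits 2 to 4 are already in the schedule, at about 20 minutes per imaging session, so the only possible addition is an image at a final contact. The downside is that some flagged images will need separate description, since they may not show the untreated course of this product.

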5.4.1 Data Collection and Follow-up for Withdrawn Subjects

Patients must document in a letter asking not to use the data collected and formalize the withdrawal. Otherwise, data up until withdrawal will be available for analysis.

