7.4.2 Investigator reporting: notifying the study sponsor

Investigators from all participating sites should report all unexpected and related adverse events, regardless of whether they are serious or not, and all unanticipated problems to the sponsor.

Any study-related unanticipated problem posing risk to subjects or others, and any type of serious adverse event, will be reported to the study sponsor by telephone within 24 hours of the event. To report such events, a Serious Adverse Event (SAE) form will be completed by the investigator and emailed to the study sponsor within 24 hours. The investigator will keep a copy of this SAE form on file at the study site. Report serious adverse events by sending via email to: [Evolus., Company Call Center: [name] ([name]), Company Email: [contact]]

Within the following 48 hours, the investigator will provide further information on the serious adverse event or the unanticipated problem in the form of a written narrative. This should include a copy of the completed Serious Adverse Event form, and any other diagnostic information that will assist the understanding of the event. Significant new information on ongoing serious adverse events should be provided promptly to the study sponsor.

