7.6 Confidentiality

Information about study subjects will be kept confidential and managed according to the requirements of the Health Insurance Portability and Accountability Act of 1996 (HIPAA). Those regulations require a signed subject authorization informing the subject of the following:

- What protected health information (PHI) will be collected from subjects in this study
- Who will have access to that information and why
- Who will use or disclose that information
- The rights of a research subject to revoke their authorization for use of their PHI.

In the event that a subject revokes authorization to collect or use PHI, the investigator, by regulation, retains the ability to use all information collected prior to the revocation of subject authorization. For subjects that have revoked authorization to collect or use PHI, attempts should be made to obtain permission to collect at least vital status (i.e. that the subject is alive) at the end of their scheduled study period.

CONFIDENTIAL

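### Section 5.4.1 lets a withdrawing subject take her adverse event data out of the analysis by letter, and it is not reconciled with Section 7.6

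*Combined protocol and SAP*

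**What the plan says.** Section 5.4.1 sets the rule for data already collected when a subject leaves: "Patients must document in a letter asking not to use the data collected and formalize the withdrawal". The next sentence gives the default: "Otherwise, data up until withdrawal will be available for analysis". Read together, a letter takes the earlier data out of the analysis and no letter leaves them in. Adverse event data are not treated separately.

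Section 7.6 covers a neighbouring situation. It opens with "In the event that a subject revokes authorization to collect or use PHI" and says that the investigator "retains the ability to use all information collected prior to the revocation of subject authorization". Neither section refers to the other.

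Three other sections concern the adverse event itself:

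- Section 5.4 foresees withdrawal because of harm ("Subjects may also be withdrawn following an adverse event that does not allow them to continue with the study") and provides a last check: "Subjects who withdraw early will have one final communication to collect final evaluations and assess for adverse events".
- Section 7.2 states: "All adverse events occurring during the study period will be recorded".
- Section 7.4.2 says that a serious adverse event "will be reported to the study sponsor by telephone within 24 hours of the event".

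The statistical plan (Section 6) sets the sample size at 10 and describes the analysis as descriptive. It defines no safety analysis set and no adverse event summary, and it has no rule for subjects who withdraw.

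**The concern.** Section 5.4.1 is the only text that decides whether a withdrawn subject's data enter the results, and it leaves that decision with the subject after she knows how she fared. Section 9.1 names lumps, skin necrosis and loss of vision among the possible harms, and notes that the facial images identify the subject. A woman with a poor result therefore has an understandable reason both to leave and to ask that her data not be used. Exclusion of that kind is related to the outcome, and it pushes the safety description, and with it the volume and satisfaction results, towards women without complications.

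The study has one arm and about 10 subjects. No comparison group would show an imbalance in losses, and one exclusion removes a tenth of the sample. A site that receives such a letter could look to 5.4.1 or to 7.6 and come away with different answers about the data it already holds.

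**Working it through.** **Step 1. The two rules side by side.**

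| | Section 5.4.1 | Section 7.6 |
|---|---|---|
| Trigger | Study withdrawal with a letter | Revocation of authorization for health information |
| Data collected before | Not available for analysis | Investigator may still use them |
| Nature of the rule | Restricts use | Permits use |
| Adverse event exception | None | Not needed, since all earlier data stay usable |
| Cross-reference | None | None |

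A subject who leaves and asks that her information no longer be used could reasonably be handled under either column. The protocol does not say which one governs.

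**Step 2. What still captures the event.** Section 5.4 provides an adverse event assessment at early withdrawal. Section 7.2 requires recording in the source document and the case report form. Section 7.4.2 requires a serious event to reach the sponsor within 24 hours. Section 5.4.1 limits none of these. The gap therefore opens only at the step from the recorded event to the analysed or published summary.

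**Step 3. Size of the effect in such a summary.** The plan gives no figure to reproduce: 10 subjects is stated in Section 6.1 without a derivation, and no adverse event rate is assumed.

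Inputs: n = 10 (Section 6.1). Assumption: x women have the event, and one of them sends the letter, so x/10 becomes (x − 1)/9. Intervals are exact (Clopper-Pearson) at 95%.

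- Kept, x = 1: the estimate is 1/10 = 10.0%. The lower limit is 1 − 0.975^(1/10) = 0.0025. The upper limit solves (1 − p)^10 + 10p(1 − p)^9 = 0.025, which gives p = 0.445. The interval is 0.3% to 44.5%.
- Removed: the estimate is 0/9 = 0%. The upper limit is 1 − 0.025^(1/9) = 0.336. The interval is 0% to 33.6%.

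The same calculation for other assumed counts:

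| Women with event | Data kept | One affected woman removed |
|---|---|---|
| 1 | 1/10 = 10.0% (0.3% to 44.5%) | 0/9 = 0% (0% to 33.6%) |
| 2 | 2/10 = 20.0% (2.5% to 55.6%) | 1/9 = 11.1% (0.3% to 48.2%) |
| 3 | 3/10 = 30.0% (6.7% to 65.2%) | 2/9 = 22.2% (2.8% to 60.0%) |

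The intervals overlap heavily, as they must at this size. What matters is the first row, where a type of event that occurred is no longer mentioned.

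**The case against.** A reader might infer three stronger things, and the documents support none of them.

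- *That a site cannot obey Sections 5.4.1, 7.2 and 7.6 together.* It can. Section 7.6 has a different trigger and grants an ability, not a duty, so declining to use data on request breaches nothing in it. Section 7.2 concerns recording, which 5.4.1 leaves alone. However, the way to satisfy all three is to record the event and then not use it, which is the omission at issue.
- *That the event would vanish from the safety record.* Section 5.4.1 speaks of use and of analysis, not of deletion. Assessment at withdrawal, recording, follow-up and expedited reporting all stand.
- *That a serious event would be reported to the sponsor as none observed.* A later letter does not undo a report made within 24 hours. Only the analysed or published summary is exposed.

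Further points against the concern have weight. Section 5.4 has each subject's completion status documented, so one missing woman in 10 would be visible on file. The illustration needs an adverse event, a withdrawal and a letter in the same woman, and the documents give no probability for any of these. Section 6 plans no adverse event rate, so no planned estimate changes. Whether a participant may have her data excluded is also a consent and ethics question, and the consent form was not available for this review.

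These points limit the size of the problem without removing it. Completion status on file does not tell a reader of the results that an event was left out. The lack of a planned safety summary also means that nothing else in the plan protects against the omission.

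**Conclusion.** The concern holds as an unreconciled rule with a foreseeable bias. Followed as written, Section 5.4.1 allows data already collected, adverse events included, to leave the analysis at the subject's request after her outcome is known. Section 7.6 points the other way for the closely related case of revoked authorization, and the protocol does not rank the two.

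The consequence is confined to the analysed or published results. If one affected woman sends the letter, a proportion of 1/10 becomes 0/9. This rests on that assumed scenario and on 10 women being injected; it shows what one letter can do, not how often it would happen. The matter should be corrected because one subject can change what a series of this size says about harm, and the correction is cheap.

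**What to change.** Reconcile Section 5.4.1 with Section 7.6, so that one rule governs data collected before withdrawal or revocation, and have each section refer to the other. In 5.4.1, state that:

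- adverse event data collected before withdrawal, and the count of women injected, are always kept and reported;
- all injected women form the denominator of the safety summary;
- the number of withdrawals and the number of requests to withhold data are reported alongside the results.

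Word the consent form to match, and settle this before subjects are consented, because it determines what they are told about their data.

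The cost is a sentence or two in 5.4.1, a cross-reference in 7.6 and the matching consent wording. The small downside is that a subject can no longer have her adverse event data left out of the summary. Her images and questionnaire answers may still be withheld at her request. The volume and satisfaction results could then still lose her, but the reported count of requests would make that loss visible.

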5.5 Early Termination Visits

This may be due to the subjects' own choice or the investigator's decision. If the investigator makes the decision, subjects will be contacted and reasons for study termination will be thoroughly explained.

6 Statistical Plan

6.1 Sample Size and Power Determination

The sample size of this case series will be 10 female patients between the ages 22 and 65.

6.2 Statistical Methods

Descriptive statistics will be used to describe volume changes of undereye hollows over time. The results of this study will not have true statistical significance.

6.3 Control of Bias and Confounding

All patients will be injected with the same filler product in the same locations.

6.3.1 Baseline Data

Baseline and demographic characteristics will be summarized by standard descriptive statistics (including mean and standard deviation for continuous variables such as age and standard percentages for categorical variables such as race).

CONFIDENTIAL

6.3.2 Analysis of Primary Outcome of Interest

The primary analysis of volumetric measurements will be done using the Allergan Infraorbital Hollow Scale and the Tear Trough Rating Scale.

7 Safety and Adverse Events

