2.1 Primary Objective

The primary objective of the study is to quantify and describe under eye volume changes over time after infraorbital hyaluronic acid filler injections.

3 Investigational Plan

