3.3 Study Measures

3D photogrammetry imaging of each subject at the pre-determined time points will be obtained using the VECTRA M3 (Canfield Scientific, Inc., Fairfield, NJ) which allows for volumetric measurements. Three-dimensional coordinates will be calculated to generate each subject's topographic configuration, displacement, and volume of each detected point on the surface of the face relative to its original reference image.

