3.4.2 Secondary Study Endpoints

- 1) Correlation of patient satisfaction with undereye volume changes as determined by PRO's (via FACE-Q)
- 2) Allergan Infraorbital Hollow Scale

TABLE 1. Allergan Infraorbital Hollows Scale Descriptors		
Grade	Term	Descriptor
0	None	No visible hollowing or volume loss medially or laterally
1	Minimal	Presence of hollowing with some volume loss medial to the mid-pupillary line; smooth lateral lid-cheek transition
2	Moderate	Defined hollowing extending laterally beyond the mid-pupillary line with moderate volume loss; smooth lateral lid-cheek transition with mild volume loss
3	Severe	Defined hollowing extending laterally beyond the mid-pupillary line with moderate volume loss creating a defined groove along the lid-cheek junction
4	Extreme	Defined hollowing extends from medial to lateral canthus; severe volume loss creates a marked step along the lid-cheek junction

[figure not shown]
[figure not shown]

Figure 2. Assessment guide for the Allergan Infraorbital Hollows Scale.

- 3) Tear Trough Rating Scale

TTRS

The tear trough was assessed based on multiple characteristics defined by a novel TTRS. The multicontoured area of the tear trough is the additive product of multiple factors. Each separate component was evaluated individually, and the score was totalled. The factors accounted for the evaluation scale are described below:

- Depth of the trough – distance from the anterior lacrimal crest to the depth of the trough; each millimeter of depth is given 1 point (i.e., a prominent trough with a 3-mm depth is given 3 points)
- Hyperpigmentation – dyspigmentation, while not directly contributing to the depth of the trough, creates an illusion of depth; no hyperpigmentation is given 1 point; mild is given +2 points; moderate pigmentation is given +3 points; and intense or deep hyperpigmentation is given 4 points; subdermal dark casting caused by venous pooling can be graded as hyperpigmentation.
- Prolapse of nasal fat pads/pockets – prominent prolapse of the nasal fat pad accentuates the depth of the trough and was rated as mild (1 point), moderate (2 points), or severe (3 points).
- Lower eyelid skin rhytidosis accentuates the fatty prolapse and the depth of the trough – skin rhytidosis is rated 1+ to 4+ (mild, moderate, advanced, severe – according to Glogau's scale); 1+ is given 1 point, and 4+ is given 4 points

Because tear troughs are often asymmetric, both sides should be evaluated individually.

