5.1 Screening

The screening visit involves patient evaluation of inclusion and exclusion criteria. This information is readily available on the intake visit and does not deviate from standard of care for a clinic visit, including

CONFIDENTIAL

age and past medical history. Once patients are deemed eligible, the process of informed consent will begin. Informed consent will take place.

5.2 *Study Intervention or Observational Phase*

5.2.1 **Visit 1 (sometimes referred to as the baseline visit)**

Visit 1 involves screening, consent, baseline imaging, randomization, intervention. The subject will be photographed using 3D imaging to measure baseline undereye volume. After these images, subjects will complete a FACE-Q questionnaire and then be injected with Juvéderm Volbella XC filler in the infraorbital region according to a preset injection plan per FDA approved administration guidelines. Medication will be prepared as described on the FDA approved medication guide. A second set of 3D images will be taken after filler injection to measure starting infraorbital volume.

5.2.2 **Visit 2**

Visit 2 which will occur 14-days post-injection, will consist of a repeat of the above measurements using 3D imaging. Subjects will also complete the FACE-Q via electronic REDCap survey and communicate any questions or concerns.

5.2.3 **Visit 3**

Visit 3 which will occur 30-days post-injection, will consist of a repeat of the above measurements using 3D imaging. Subjects will also complete the FACE-Q via electronic REDCap survey and communicate any questions or concerns.

5.2.4 **Visit 4**

Visit 4 which will occur 90-days post-injection, will consist of a repeat of the above measurements using 3D imaging. Subjects will also complete the FACE-Q via electronic REDCap survey and communicate any questions or concerns.

TABLE 1 SCHEDULE OF STUDY PROCEDURES

	Baseline Visit 1	Intervention	Follow-up Visit 2 Day 14	Follow-up Visit 3 Day 30	Follow-up Visit 4 Day 90
Visit Window	Day 1	Day 1	Day 14 ± 5	Day 30 ± 5	Day 90 ± 7
Eligibility	X				
Informed Consent	X				
Demographic	X				
Medical History	X				
Consultation	X				
Vectra Photography		X (pre and post injection)	X	X	X

CONFIDENTIAL

FACE-Q		X	X	X	X
Adverse Events		X	X	X	X

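### Section 6.3.2 gives the primary analysis of volume to two secondary rating scales that yield no volume, so the 3D-imaging primary endpoint has no matching primary analysis

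*Combined protocol and SAP*

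**What the plan says.** The objective, the measurement method and the endpoint agree with one another.

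- Section 2.1: "The primary objective of the study is to quantify and describe under eye volume changes over time after infraorbital hyaluronic acid filler injections".
- Section 3.3 names the VECTRA M3 as the instrument. Its output includes displacement and "volume of each detected point on the surface of the face relative to its original reference image".
- Section 3.4.1: "The primary endpoint is volume changes of the infraorbital area over time after injection of filler quantified using 3D facial imaging measurements".
- Section 5.2.1 (Visit 1): "The subject will be photographed using 3D imaging to measure baseline undereye volume". Imaging is repeated after injection on Day 1 and on Days 14, 30 and 90.

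Section 3.4.2 lists the Allergan Infraorbital Hollow Scale and the TTRS as secondary endpoints 2 and 3.

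Section 6.3.2, which is headed as the analysis of the primary outcome, then says: "The primary analysis of volumetric measurements will be done using the Allergan Infraorbital Hollow Scale and the Tear Trough Rating Scale". It does not mention 3D imaging.

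Two other places touch on the analysis of volume. Section 6.2 and the Study Summary both say that descriptive statistics will be used for volume change over time. Neither names a reference image, a time point, a unit of analysis or a summary statistic.

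**The concern.** The section that designates the primary analysis points to variables other than the primary endpoint. In a case series with no hypothesis test, the reported primary outcome is the main product of the study, so the plan has to say without contradiction which variable that is. As it stands, one analyst could follow 3.4.1 and report volume change while another followed 6.3.2 and reported two clinical scales. Both could say that they kept to the protocol.

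The scales are not interchangeable with volume. A TTRS total can change through pigmentation or rhytidosis while depth stays the same. A real volume change that stays within one Allergan grade would be recorded as no change.

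**Working it through.** The plan gives no figure to reproduce here. The sample size of 10 in 6.1 has no alpha, power, effect size or SD behind it. The check is a comparison of sections, followed by arithmetic on the scale as printed.

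**Step 1: which sections agree.**

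| Section | Outcome or analysis named |
|---|---|
| 2.1 Primary objective | Volume change over time |
| 3.3 Study measures | VECTRA 3D imaging |
| 3.4.1 Primary endpoint | Volume change by 3D imaging |
| 5.2.1 Visit 1 | 3D imaging for baseline volume |
| 6.2 and Study Summary | Descriptive statistics of volume change, method not named |
| 3.4.2 Secondary endpoints | Allergan scale, TTRS |
| 6.3.2 Primary analysis | Allergan scale, TTRS |

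Section 6.3.2 is the only outlier, and it is the only section that names a primary analysis.

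**Step 2: does either scale give a volume?** The Allergan scale in 3.4.2 takes the integers 0 to 4. Its descriptors refer to volume loss, but only in graded words. For the TTRS, "Each separate component was evaluated individually, and the score was totalled". Its one dimensional item is a length: "each millimeter of depth is given 1 point". Neither scale has a unit of volume.

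**Step 3: how far a TTRS total can move at fixed depth.** The point rules in 3.4.2 for the items other than depth are:

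- hyperpigmentation, 1 to 4 ("no hyperpigmentation is given 1 point; mild is given +2 points", rising to 4);
- fat-pad prolapse, 1 to 3;
- rhytidosis, 1 to 4.

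Minimum: 1 + 1 + 1 = 3. Maximum: 4 + 3 + 4 = 11. Spread: 11 − 3 = 8 points.

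At the document's own example depth of 3 mm, which scores 3 points:

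- the total runs from 3 + 3 = 6 to 3 + 11 = 14;
- the depth share runs from 3/14 = 21% to 3/6 = 50%.

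Section 3.4.2 gives no score for absent prolapse. If absence scores 0 (an assumption), the minimum is 1 + 0 + 1 = 2, the total runs from 5 to 14, the spread is 9 points, and the depth share runs from 21% to 3/5 = 60%.

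**Step 4: how much primary data is bypassed.** There are four post-injection image sets per patient (Day 1 after injection, Days 14, 30 and 90). With about 10 patients and one value per patient at each time point, that is 10 × 4 = about 40 changes from baseline. Counted per eye it is 10 × 2 × 4 = about 80. Section 6.3.2 analyses none of them as a volume.

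**Step 5: are the scales scheduled?** The schedule table in 5.2 has rows for Vectra photography, FACE-Q and adverse events, but none for either scale. The visit text mentions only imaging and FACE-Q. The scales might be scored from stored images, but the plan does not say so.

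**The case against.** The strongest reply is that volume is analysed. Section 6.2 and the Study Summary promise descriptive statistics of volume change, which for an untested series of about 10 patients could be called an analysis of the primary endpoint. That stands in part: it would be wrong to say that the plan never analyses volume. But the general sentence does not designate a primary analysis, and it does not override the section written for that purpose.

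A second reply is that 6.3.2 may be a clumsy way of saying that VECTRA volumes will be interpreted against the scales. This is possible, but it is not the natural reading. If it was meant, the sentence still needs rewriting.

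A third reply is that the TTRS figures are extremes across hypothetical patients, not changes within a patient over 90 days, and that pigmentation may not be independent of volume, since section 1.1 links volume loss to shadowing and darkness. This is fair as a limit on what the figures show. They establish that the total is not a measure of volume. They do not estimate a bias.

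Finally, the intent can be recovered from 2.1, 3.3 and 3.4.1, and no primary data are lost because imaging is scheduled throughout. Both points are true. They make the correction easy, but they do not make the text consistent.

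**Conclusion.** The concern holds, and 6.3.2 must be corrected before analysis. It names two secondary scales as the primary analysis, and neither measures the endpoint defined in 3.4.1. The general commitment in 6.2 does not repair this.

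The consequence is that the wrong variables would be reported as primary, with all of the roughly 40 planned volume changes left outside the named primary analysis. That count assumes about 10 patients, complete imaging and one value per patient per time point. The 8-point TTRS spread at equal depth follows from the printed point rules; the 9-point version rests on the assumption that absent prolapse scores 0. No hypothesis test is planned, so alpha and power are unaffected, and no size of bias is claimed.

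The missing scoring schedule for the two scales is a smaller, separate gap.

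**What to change.** Replace 6.3.2 with text along these lines:

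> The primary analysis is a descriptive summary (for example n, mean, SD, median and range) of the change in VECTRA infraorbital volume from the pre-injection image to the Day 1 post-injection image and to Days 14, 30 and 90. Change from the Day 1 post-injection image may also be reported to describe retention. The Allergan Infraorbital Hollows Scale and the TTRS are analysed as secondary endpoints.

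Two details should be settled in the same edit:

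- **Unit of analysis.** State whether it is the eye or the patient.
- **Reference image.** Confirm the choice. The pre-injection image fits 3.3, but 5.2.1 also describes the post-injection images as giving a starting volume, so the investigators should say which reference is primary.

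Then add to 5.2 and its schedule table when the two scales are scored, by whom, and whether at the visit or from stored images.

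The cost is one rewritten paragraph and matching schedule text. It needs no extra patients, visits or images, and scoring of both scales is already implied by their place among the secondary endpoints. The sample size does not change.
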